#### **1.2.4 Study BN29854 (OLEOS)**

The 12-month analysis of the OLEOS BN29854 study ([Muntoni et al. 2017](#)) demonstrated that olesoxime was generally safe and well tolerated at the dose assessed, with a safety profile comparable to placebo groups of previous studies. Despite a substantial decline in MFM D1 + D2 score (>2 points/year) since stopping study drug at the end of the previous clinical trial (median 3 years), the observed treatment difference between placebo and olesoxime was maintained at OLEOS baseline. Olesoxime sustained motor function over 12 months in patients treated open-label in the OLEOS study. These data suggest that olesoxime offers the potential to provide meaningful clinical benefit to patients with SMA by preventing loss of motor function.

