### **1.3 STUDY RATIONALE**

This study is a Phase II trial for SMA patients who participated in previous studies TRO19622CLEQ1275-1 and/or TRO19622CLEQ1115-1. The current study includes collecting retrospective data between last visit of the above mentioned trials and screening period of this study. As the last patient of study TRO19622CLEQ1275-1 received the last dose in October 2013, the retrospective data collection will serve to understand the disease course of SMA patients after withdrawal of olesoxime treatment for at least 2 years.

The study's main period is an open-label, single arm period in which the patients will receive olesoxime *at the dose of 10 mg/kg BID*, and it will serve to further characterize the safety, tolerability and effectiveness profile of olesoxime in SMA. The outcomes of the study may be compared to natural history data of similar population and outcomes.

*The study was initiated at a dose of 10 mg/kg QD; after Protocol BN29854, Version 4 is in effect, the dose will be increased from 10 mg/kg QD to 10 mg/kg BID with the aim of increasing the exposure to olesoxime and thereby increasing a possible therapeutic benefit of olesoxime, while maintaining appropriate safeguards using a thorough clinical safety monitoring plan. The total daily dose in this study will not exceed 2000 mg. For details on the dose increase rationale, see Section 3.3.1.*

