### **3.1.1.3      Treatment Period**

*Patients who have consented to the dose increase specified in Protocol BN29854, Version 4 will receive liquid formulation of olesoxime at a dose of 10 mg/kg BID either orally or via a naso-gastric or gastrostomy tube with breakfast and dinner, preferably at the same time of the day throughout the study. If drug administration does not coincide with one of the scheduled meals, a snack should be taken prior to drug administration. Preferably there should be at least 10 hours between the morning and evening dose. The total daily dose in this study will not exceed 2000 mg. Therefore, patients with a body weight >100 kg will receive a dose of 1000 mg BID. This*

*maximum dose of 2 g/day forms the basis of the technical IMP specifications in the drug manufacturing process and cannot be exceeded for this reason.*

*Patients who have not consented to the dose increase specified in Protocol BN29854, Version 4 will be administered olesoxime at 10 mg/kg QD orally or via a naso-gastric or gastrostomy tube with the main meal throughout the study.*

**Patients' visits will occur at 3 months, 6 months, 9 months, 12 months, and every 6 months thereafter for medical examination, and safety and efficacy assessments.**

*Related to the dose increase per Protocol BN29854, Version 4, one or two additional visits will occur (see the Schedule of Assessments in [Appendix 1](#)). For treatment period duration, please refer to Section [3.2](#).*

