##### **Procedure for Dose Increase**

*All patients are asked to attend an unscheduled dose increase visit as early as possible, to increase their dose to the recommended level. Patients will be required to re-consent prior to dose increase and related assessments. If the medical condition of a patient does not allow an additional study visit or the date of the next regular study visit is scheduled close to when Protocol BN29854, Version 4 becomes in effect, the option to increase the dose at the next scheduled study visit will be offered.*

*Dose increase visit procedure options:*

- 1. Patients attend an additional dose increase visit to increase their dose to the recommended level as early as possible. Only the specified assessments for the dose increase visit will be performed (see the Schedule of Assessments in [Appendix 1](#)).*
- 2. Patients attend their next scheduled regular visit to increase their dose to the recommended level. Specified assessments for the dose increase visit (see [Appendix 1](#)) and scheduled assessments for the regular visit will be performed.*

*Prior to the dose increase, specified assessments need to be performed (see Schedule of Assessments in [Appendix 1](#)). These assessments include 24-hour Holter ECG monitoring (see Section [4.4.9.1](#)) as well as blood sampling for PK and biomarker assessments (Section [4.4.8.1](#)). If a patient performs the procedure for dose increase as part of a regular study visit and an ECG assessment is scheduled for this visit, only the 24-hour Holter ECG needs to be performed. If PK and biomarker samples are scheduled for this regular study visit, the relevant sample types need to be collected only once.*

*Blood samples shall be taken predose. Therefore, before attending the dose increase visit, patients should be reminded not to take the drug at home, as they will have it administered with their next meal after the assessments are conducted.*

*Starting on the day after the removal of the Holter ECG monitor, patients will receive olesoxime at a dose of 10 mg/kg to be taken twice daily with breakfast and dinner.*

*In addition to the dose increase procedure, the investigator will fill out the OFS and the CGI-C. The OFS is a brief survey designed to explore potential benefit of olesoxime on fatigability (i.e., endurance). The CGI-C assesses the clinician-reported change in the patients overall health status.*

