## **6. STATISTICAL CONSIDERATIONS AND ANALYSIS PLAN**

### **6.1 ANALYSIS POPULATIONS**

#### **Safety Population**

The safety population will consist of all patients who received at least one dose of study medication. All safety data will be summarized based on the safety population.

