## **6.6 PRIMARY ANALYSES**

Safety analysis will be based on the safety population.

Safety variables (e.g., laboratory tests, vital signs, and ECG) will be summarized for each assessment time (including follow-up) using descriptive statistics. *The data will be summarized by the dose being taken at the time of the assessment (10 mg/kg QD or 10 mg/kg BID). Data from the two 24-hour Holter ECG assessments will also be summarized.*

Adverse events will be coded and summarized by body system and preferred term. Adverse events will also be summarized by intensity and relationship to trial treatment as assigned by the investigator. Serious adverse events will be summarized separately. *Adverse events will be summarized by the dose being taken at the onset date of the adverse event.*

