### Schedule of Assessments (cont.)

- l Only assessed in patients aged 9–17 years at Visit 1 and annually thereafter.
- m For a list of all safety laboratory assessments, please refer to Section 4.4.8.
- n For patients aged 6–17 years, *includes* thyroid hormones (free thyroxine T4 and thyroid-stimulating hormone); and for patients aged 12–17 years or younger who have menses, also includes estradiol, follicle-stimulating hormone, *and* luteinizing hormone. Hormone assessments should occur every 12 months.
- o Urine pregnancy tests will be performed at all visits. If a urine pregnancy test is positive, it must be confirmed by a serum pregnancy test.
- p Includes dipstick (pH, specific gravity, glucose, protein, ketones, blood). If deemed necessary for further investigation, the treating physician can request microscopic examination (sediment, RBCs, WBCs, casts, crystals, epithelial cells, bacteria). Urinalysis should occur every 12 months.
- q *Should be performed predose.*
- r Actual PK sampling times must be documented. Actual date and time of study drug administration for the preceding two doses (except on Visit 1) must be documented in the eCRF.
- s Separate whole blood samples for SMN protein and SMN2 mRNA assessment. Please refer to Section 4.4.8.1.
- t Serum sample for fluid biomarkers. Please refer to Section 4.4.8.1.2.
- u In case it was not possible to collect *the baseline* sample during Visit 1, a sample for clinical genotyping should be drawn at the next visit. Please refer to Section 4.4.8.2.
- v ECG should be performed at screening and Visit 2 and then yearly from start of treatment.
- w *If dose increase visit is performed at a scheduled visit, ECG does not need to be performed since a 24-hour Holter ECG monitoring is being performed.*
- x Please refer to Section 4.4.10 for age-specific assessment and details. Complete before all other assessments during the study visit.
- y Please refer to Section 4.4.11 for details on the Caregiver-Reported Outcomes.

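### The by-dose adverse-event tables mix dose with time on study, selection and length of follow-up, so they cannot show whether going from QD to BID adds harm

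*Protocol*

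**What the plan says.** Protocol Section 6.6 assigns each adverse event (AE) to a dose: "Adverse events will be summarized by the dose being taken at the onset date of the adverse event". Laboratory tests, vital signs and ECGs are split by the dose at the assessment, and the two Holter recordings are also summarised.

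Who contributes to each column follows from other sections:

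- Protocol 1.3: "The study was initiated at a dose of 10 mg/kg QD".
- Protocol 6.1: "The safety population will consist of all patients who received at least one dose of study medication".
- Protocol 3.1.1.4: "Patients will be required to re-consent prior to dose increase and related assessments". Patients who do not consent stay on QD.

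Under Protocol 3.1.1.3, "visits will occur at 3 months, 6 months, 9 months, 12 months, and every 6 months thereafter". Footnote v of Appendix 1 adds: "ECG should be performed at screening and Visit 2 and then yearly from start of treatment". From Visit 5, a telephone call follows each visit by 12 weeks (Protocol 4.4.18, Appendix 3). Patients who increase the dose have a further safety visit 4 weeks later.

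The SAP has no by-dose method. Its Sections 2 and 3.1 describe QD only. Section 4.6.2 counts each patient once per event term and gives the total number of AEs. The only rate per patient-year (Section 4.4.2.4) is for SMA-related complications, set against the NatHis-SMA cohort and not split by dose.

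**The concern.** The by-dose tables will be read as the answer to whether doubling the daily dose adds harm. The two columns differ in three ways besides dose.

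- **Time on study.** QD time includes the start of treatment in this study. BID time always comes later. Version 4 already cites "The 12-month analysis of the OLEOS BN29854 study", which suggests that most BID time falls after Week 52.
- **Selection.** Patients who stopped early, for whatever reason, count only under QD, as do decliners. BID patients had stayed on QD and agreed to the increase.
- **Length of follow-up.** A percentage of patients with an event grows with time at risk, which will differ between the doses.

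There is also a counting problem. Under Protocol 5.3.5.3 a persistent AE is recorded once. An event that starts on QD and worsens after the increase therefore stays in the QD column by its onset date.

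BID could look as safe as QD, or safer, although the increase adds harm. It could also look worse when it does not.

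**Working it through.** **Inputs.** The earlier randomised trial (Protocol 1.2.2) had 165 patients. Over 24 months, serious adverse events (SAEs) occurred in 34 (31.5%) on olesoxime QD and 29 (50.9%) on placebo, 63 (38.2%) in all. Of 119 of its patients sampled at baseline of the present study, 81 had received olesoxime and 38 placebo. The documents do not give time on each dose, the number switching or the number withdrawing. I assume 1 to 2 years on QD and 0.5 to 1.5 years on BID.

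**1. Source figures.** 34/108 = 31.5%, 29/57 = 50.9% and 63/165 = 38.2%. The denominators 108 and 57 are inferred from the percentages; they sum to 165.

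**2. Effect of unequal time alone.** With a constant hazard, h = −ln(1 − 34/108)/2 = 0.189 per year. The percentage of patients with an SAE after T years at rate ratio RR is 1 − exp(−h × RR × T).

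| QD years | BID years | QD % | BID %, RR 1 | BID %, RR 1.25 | BID %, RR 1.5 | RR at which BID looks equal |
|---|---|---|---|---|---|---|
| 1.5 | 1 | 24.7 | 17.2 | 21.0 | 24.7 | 1.5 |
| 1.5 | 0.5 | 24.7 | 9.0 | 11.1 | 13.2 | 3.0 |
| 1 | 1 | 17.2 | 17.2 | 21.0 | 24.7 | 1.0 |
| 1 | 1.5 | 17.2 | 24.7 | 29.8 | 34.6 | 0.67 |

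The last column is QD years divided by BID years. In the first row a true 25% increase looks like a reduction. In the last row no increase at all looks like harm.

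**3. What a patient-year rate leaves.** It removes step 2 but not start-up effects or selection. Suppose a share f of patients has m times the usual rate in the first 0.25 year, frailty has variance θ, and cumulative AE-driven withdrawal before the increase is L. BID then looks equal to QD at a true rate ratio of

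[1 + f(m − 1) × 0.25/T_QD] × (1 + θL).

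With f = 38/119 = 0.32, m = 2, T_QD = 1.5, θ = 1 and L = 0.05, this is 1.053 × 1.05 = 1.11. I varied m from 1.5 to 3, T_QD from 1 to 2 years and L from 0 to 0.15, with θ = 1. The result is 1.02 to 1.33 if the excess affects only former placebo patients, and 1.06 to 1.72 if it affects everyone. None of f, m, θ or L is a trial figure except the 38/119.

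**4. Contact and sampling.**

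- AE contacts: 4 in year one (Weeks 13, 26, 39, 52). Later also 4 per year (2 visits and 2 calls), plus the 4-week visit on BID.
- Scheduled laboratory and vital-sign visits: 4 in year one, then 2 per year, plus the visits around the increase.

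Scheduled AE contact is thus not reduced. Only clinic sampling becomes sparser.

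**5. The 4-week sample.** SAP 4.6 keeps one record per visit window, the one closest to the scheduled day. If the increase is made at Visit 6 (Day 547), the 4-week sample falls at about Day 547 + 28 = Day 575. That lies in the same window (Days 457 to 638) as the QD sample and loses to it, unless selection is made within dose. The SAP has no such rule.

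**The case against.** The plan promises description, without formal testing, and several stronger readings that a reader might draw do not stand.

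- **Safety follow-up is halved on BID.** Not for AEs: they are sought at every contact (Protocol 5.3.1), and the calls keep contact at about 4 per year.
- **Sparser sampling biases the laboratory and ECG tables.** Per-visit means and percentages do not depend on samples per year. Only overall shift tables and listings do. Scheduled ECGs were never 13-weekly. Counting the Holter recordings, QD over 1.5 years has 3 (2.0 per year) and the first BID year has 2 (2.0 per year).
- **QD time is first exposure.** For the 81 former olesoxime patients among the 119 sampled it is re-exposure.
- **The by-dose tables are the only planned look at dose and harm.** The Holter recordings are paired within patients, and Protocol 6.9 plans exposure-response analyses that include AEs, laboratory tests and ECG.
- **The bias must favour BID.** Disease progression, awareness of a higher dose, closer monitoring after the increase, or longer BID follow-up would push the other way.

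All of this stands, and it limits the point. It does not remove it. The Holter comparison covers rhythm at 4 weeks. The exposure-response work is graphical, with modelling only if a relationship appears, and is reported separately. Neither gives a within-patient comparison of AEs or laboratory values.

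**Conclusion.** The point holds for the AE contrast by dose, which is confounded by construction and has no planned adjustment or within-patient counterpart. It can hide a dose effect or create one. The documents do not settle the direction.

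The size depends on unstated exposure. In the case of 1.5 years on QD and 1 year on BID, any true increase below 50% shows BID with the lower percentage; a 25% increase appears as 21.0% against 24.7%. This assumes a constant hazard carried over from the earlier trial and the same follow-up for everyone within a dose. After adjustment for patient-years, the remaining distortion is smaller in most of the assumed settings, but it cannot be sized from the documents.

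That BID time falls mostly after Week 52 is an inference: no switch dates are given, and a CGI-C scheduled at Visit 5 leaves room for earlier switches. The change is worth making because safety is the primary objective, but the existing tables need not be dropped.

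**What to change.** In Protocol 6.6 and SAP 4.6.2, 4.6.4 and 4.6.6:

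1. Bring the SAP into line with both doses. Keep the by-dose tables as descriptive, with a note that population and schedule differ.
2. Add AE rates per patient-year by dose.
3. Add a within-patient comparison in switchers over equal windows, 26 weeks before and 26 weeks after the first BID dose, giving patients with events and event rates.
4. Pair the pre-increase and 4-week laboratory values, and the last QD ECG with the first BID ECG.
5. Count an AE that began on QD and worsened after the increase in the BID window.
6. Report deaths and withdrawals separately, because a switcher cannot have either in the earlier window. Flag patients whose earlier window reaches back before Week 52.

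**Cost.** Wording and one further set of tables, almost wholly from data already collected. Item 5 needs a date of worsening. Protocol 5.3.5.3 mentions a date only for an event becoming serious, so a derivation rule or an added field may be needed.

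**Downsides.** The windows are less precise for rare or late events, which remain in the full tables. The survivor effect in the earlier window works against BID. Visits are not fully balanced when the increase is made at a regular visit (Option 2 in Protocol 3.1.1.4).

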## **6.7           SECONDARY ANALYSES**

The change from baseline in MFM D1+D2 and MFM Total Score will be summarized at each visit using descriptive statistics. *The data will be summarized by the dose being taken at the time of the assessment.* Mean changes and 95% confidence intervals over time will be presented graphically. Summary statistics by age and SMA type will also be provided.

Where available, similar descriptive statistics may be presented for the Natural History Data.

Statistical modelling approaches may be used to explore the effects of differences in baseline covariates. Details will be provided in the SAP.

The incidence of disease associated medical complications and procedures will be summarized. *The data will be summarized by the dose being taken at the onset date of the event.*

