*Attempts to increase the systemic exposure of olesoxime by increasing the daily dose from 10 mg/kg QD to 20 mg/kg QD (using a solution formulation) produced a marginal (~20%) increase in  $AUC_{0-\infty}$ . The limited increase in bioavailability is thought to be due to saturable absorption of olesoxime. However, when the 20 mg/kg dose was divided into two doses, 10 mg/kg each, administered approximately 12 hours apart, an increase in the  $AUC_{0-\infty}$  of 100% was observed, while  $C_{max}$  was only increased by ~20%. The preliminary results of the study also indicated that a dose of 30 mg/kg of olesoxime in suspension formulation divided into two doses (15 mg/kg each) resulted in an increase of ~120% in AUC and ~56% increase in  $C_{max}$ , compared with a single dose of 10 mg/kg as suspension. Therefore, although a dose of 10 mg/kg BID in suspension form was not tested in Study BP39378, this dose is projected to produce a ~100% increase in AUC and the average steady-state plasma concentration of olesoxime, while  $C_{max}$  should only increase by 20% to 30%. The increase in exposure is assumed to lead to a clinically meaningful increase in motor function for patients (2-point increase in the MFM D1 + D2 efficacy score) as detailed before.*

*The total daily dose in this study will not exceed 2000 mg. Thus, for patients with body weight >100 kg, the administered dose will be 1000 mg BID. The maximum dose of 2 g/day forms the basis of the technical IMP specifications in the drug manufacturing process and cannot be exceeded for this reason.*

*The drug will be provided as liquid suspension formulation of olesoxime (100 mg/mL) for oral administration or via gastrostomy tube. Due to the weight-based dosing, it is required that body weight be measured and recorded at every study visit. The study drug should be administered BID orally or via a naso-gastric or gastrostomy tube with breakfast and dinner, preferably at the same time of the day throughout the study.*

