#### **4.4.12 Clinical Global Impression of Change**

*The CGI-C is a single-item measure of change in global health that uses seven response options: Very Much Improved, Much Improved, Minimally Improved, No Change, Minimally Worse, Much Worse, and Very Much Worse. It is a widely used endpoint in clinical trials across a variety of disease areas. Clinicians will score patients using this scale based on their impression of change in the patient's global health since baseline. To enhance inter-rater consistency, an instructions document (developed with input from clinical experts) will be provided, which includes examples for each of the response options.*

*The same clinician should complete the CGI-C at all specified visits for an individual patient. The CGI-C will be administered at the dose increase visit and study Visits 5, 6, and 7.*

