## **6.12 EXPLORATORY ANALYSES**

The effect of olesoxime on the disease progression time-course will be investigated by applying model based approaches using, as appropriate, a disease progression model accounting for the time course of disease status with time being a continuous variable. The results will be reported in a document separate from the clinical study report.

Responder rates, where a responder is defined as no worsening from baseline in MFM D1 + D2, will be summarized *by the dose being taken at the time of the assessment.*

Change from baseline in FVC will be summarized *by the dose being taken at the time of the assessment.*

*The CGI-C responses at each assessment visit will be summarized by the dose being taken at the time of the assessment. Clinicians will score patients using the CGI-C based on their impression of change in the patient's global health since baseline.*

*Smartphone sensor data collected as part of the digital biomarker approach will be analyzed. Patient adherence will be evaluated. From the sensor data, features will be developed for each smartphone-based test and correlated with the MFM and other clinical endpoints. Further exploratory analyses may be conducted. The results will be separately reported from the clinical study report.*

For further exploratory analyses, please refer to the SAP for details.

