4.4 EFFICACY ANALYSIS

As this is a single arm, open-label study no formal hypothesis testing will be performed. Data collected during the treatment phase of this study will be summarized using descriptive statistics and will be compared with observational data describing the natural history of the disease.

The baseline value will be defined as the last non-missing value recorded prior to or on the first day of the study drug (Study Day 1).

Post-baseline efficacy assessments (scheduled every 26 weeks), including assessments performed at an early discontinuation visit, will be assigned to a scheduled study visit based on the following time windows:

Visit	Study Day	Time Window (in Study Days)
V3 (Week 26)	183	Day 2 – Day 274
V5 (Week 52)	365	Day 275 – Day 456
V6 (Week 78)	547	Day 457 – Day 638
V7 (Week 104)	729	Day 639 – Day 820
V8 (Week 130)	911	Day 821 – Day 1002
V9 (Week 156)	1093	Day 1003 – Day 1184
V10 (Week 182)	1275	Day 1185 – Day 1366
V11 (Week 208)	1457	Day 1367 – Day 1548
...		

If multiple valid values for a variable are recorded in the same time window, the record closest to the scheduled study visit will be selected for summary of the data.

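### By-dose tables of MFM and FVC change use a Study Day 1 baseline, so a BID result contains the patient's whole QD period

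*Protocol*

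**What the plan says.** Protocol 6.7 sets the secondary MFM display: "The change from baseline in MFM D1+D2 and MFM Total Score will be summarized at each visit using descriptive statistics". The sentence added by Version 4 then splits it: "The data will be summarized by the dose being taken at the time of the assessment". Protocol 6.12 extends the split to two further displays that depend on baseline. One is responders ("Responder rates, where a responder is defined as no worsening from baseline in MFM D1 + D2, will be summarized", again by current dose) and the other is change in FVC. CGI-C is also split by current dose, and Protocol 4.4.12 has clinicians rate it "based on their impression of change in the patient's global health since baseline".

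The protocol does not define the efficacy baseline. SAP 4.4 does, as "the last non-missing value recorded prior to or on the first day of the study drug". Protocol 1.3 gives the dose at that point: "The study was initiated at a dose of 10 mg/kg QD". Neither document defines a baseline before BID, a change since the dose increase, or a division of change by dose period.

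The SAP has no by-dose display at all. Sections 2 and 3.1 describe a study in which everyone receives QD, and section 4.4.1 summarises MFM overall and by treatment in the previous study.

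**The concern.** Under the two rules together, the label on a BID cell describes the dose on the day of the visit, while the number in it describes everything since Day 1. For a switcher, the period before the first BID dose may be the larger part of that interval. Decline on QD would then count against BID, and improvement on QD would count for it.

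The synopsis title presents the study as evaluating effectiveness at 10 mg/kg BID, so readers of the study report will naturally take the BID column as evidence about BID. As written, no planned study-report table would let them separate the two periods.

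**Working it through.** The documents give no power, alpha or sample-size figure for this display, so there is none to reproduce. The one figure used as a yardstick is the "2-point increase in the MFM D1 + D2 efficacy score" in Protocol 3.3.1, which can be checked roughly.

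**Yardstick.** Protocol 1.2.2 gives residual concentrations of 23 and 801 ng/mL as 0.3% and 9.5% of the average trough. The implied average trough is 23/0.003 = 7,667 ng/mL to 801/0.095 = 8,432 ng/mL, or 7.67 to 8.43 mg/L. If BID adds one further average trough, the slope in 3.3.1 of 0.281 points per mg/L gives 0.281 × 7.67 = 2.15 to 0.281 × 8.43 = 2.37 points. That agrees with the rounded 2 points. The protocol gives no time horizon for this gain.

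**Inputs for the carry-over.**
- Placebo slope: -1.05 points per year (Protocol 3.3.1). Using it for patients on QD is an assumption at the unfavourable end.
- Flat course: Protocol 1.2.4 reports that function was sustained over 12 months on open-label treatment in this study, read here as a slope of 0.
- Time on QD before the switch: not stated; assumed 52, 78 or 104 weeks.
- Time on BID at the visit: not stated; assumed 26 weeks.

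**Formulae.** Change from Day 1 in a BID cell = (QD slope × years on QD) + (BID slope × years on BID). The first term is the carry-over. The QD share of the interval = weeks on QD / (weeks on QD + weeks on BID).

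| Weeks on QD + BID | QD share | Carry-over, slope 0 | Carry-over, slope -1.05/year |
|---|---|---|---|
| 52 + 26 | 66.7% | 0 | -1.05 |
| 78 + 26 | 75.0% | 0 | -1.58 |
| 104 + 26 | 80.0% | 0 | -2.10 |

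**Effect of re-baselining (78 + 26 weeks, assumed BID slope 0).**
- QD slope -1.05 per year: the Day 1 cell shows -1.05 × 1.5 = -1.58; the re-baselined cell shows 0.
- QD slope 0: both show 0.
- QD slope +0.5 per year (assumed): the Day 1 cell shows 0.5 × 1.5 = +0.75; the re-baselined cell shows 0.

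**Same-visit contrast.** At week 104, with the first set of slopes, a patient still on QD would show -1.05 × 2 = -2.10 and the switcher -1.575. The difference of 0.525 is exactly the BID-period difference, (0 + 1.05) × 0.5. So the contrast within a visit is not distorted by the baseline if the two groups are otherwise comparable.

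**Responders.** By the SAP 4.4.1 formula, one item step on MFM-32 D1+D2 is 100/75 = 1.33 points.
- Patient A gains two steps on QD (+2.67) and loses one on BID (-1.33). Net +1.33: counted as a BID responder.
- Patient B loses two steps on QD (-2.67) and regains one on BID (+1.33). Net -1.33: counted as a BID non-responder.

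The mean QD change is zero, yet each patient is classified opposite to the course on BID.

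**The case against.** A reader might infer that the amendment was designed to test BID against QD and that its main table fails at that. The documents do not support this. Protocol 1.2.3 and 1.3 give the aim as raising exposure and possible benefit, no objective in section 2 compares the two doses, and Protocol 6.1 rules out formal hypothesis testing. The 2-point gain is part of the dose rationale and is not an endpoint target.

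A reader might also take a loss of 1 to 2 points as the expected distortion. That too goes beyond the text. The -1.05 slope comes from placebo patients, and Protocol 1.2.4 describes sustained function on QD. Nil is a supportable value, and the direction is not fixed.

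The strongest objection is that the table is by visit. QD and BID cells at one visit share the same time since Day 1, so their difference would reflect only the BID period in comparable groups. The arithmetic bears this out. What remains is that dose depends on consent and on when the switch visit falls (Protocol 3.1.1.4), so the groups are not comparable. The BID cell can also mix different times on BID. Re-baselining does not cure that selection.

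The exposure-response work (Protocol 6.9) and the continuous-time disease progression model (6.12) could separate the periods. They are exploratory and reported outside the study report, so they leave these tables as they are.

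On CGI-C, a rating at the dose increase visit is already planned. BID starts only after the Holter monitor is removed (3.1.1.4), so that rating is made before BID and gives a reference. Scheduled ratings end at Visit 7, so a patient who switches at or after that visit has none on BID. This is a separate scheduling matter, and the documents do not show how many patients it affects.

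**Conclusion.** The point holds as a defect of labelling and baseline. A BID cell for MFM change, MFM responder status or FVC change, read alone or against earlier QD visits, mixes QD-period with BID-period change, and no planned study-report table corrects it.

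For mean MFM D1+D2 the carry-over runs from 0 (flat on QD) to -2.10 points (placebo slope for an assumed two years on QD). At that extreme it is about the size of the expected 2-point gain. Improvement on QD would reverse the sign. Responder misclassification does not depend on the mean QD slope.

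Part of the cause is that the two documents do not match: the by-dose rule is in the protocol, while the baseline rule is in a SAP still written for QD only. It would be wrong to conclude that a corrected baseline yields an unbiased BID-versus-QD comparison.

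**What to change.** 1. Reconcile SAP sections 2, 3.1 and 4.4 with Protocol Version 4, and state the rules for any by-dose display.
2. For BID summaries, define the BID baseline as the last MFM and FVC on or before the first BID dose. Tabulate change and responder status by time since the dose increase.
3. Keep change from Day 1 as the overall display that SAP 4.4.1 already plans. Label any by-dose split of it as not estimating the BID effect, and note that dose group depends on consent and switch timing.
4. For CGI-C, show ratings after the increase beside the rating made at the dose increase visit. This needs no schedule change. Re-anchoring the item or continuing it beyond Visit 7 would alter Protocol 4.4.12 or Appendix 1. That is an optional, separate amendment.

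Items 1 to 3 cost SAP text, wording in Protocol 6.7 and 6.12, and a few tables. No new MFM or FVC is needed, because after Week 52 both are done every 26 weeks. The drawback is that Appendix 1, as it reads in the text available, does not mark MFM at a stand-alone dose increase visit. The BID baseline may then be up to about 26 weeks old, leaving up to 1.05 × 0.5 = 0.525 points of QD change at the placebo slope. That is about a quarter of the 2-point yardstick, but less than the carry-over from Day 1. When the switch falls on a regular visit with MFM, the gap closes.
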